### **10.5.2 Secondary Endpoints**

The secondary endpoints for subjects will be analysed using a one way ANOVA for repeated measures model with Bonferroni corrected post hoc measurements. The ANOVA model will use all available data at 30 min and 90 min post dose with Vas Scores as dependent variables and time points as independent variable.

The mean VAS scores with the associated standard errors will be displayed, Estimated differences from baseline along with corresponding 95% CIs and p-values will also be presented.

To analyse post-recovery change in C2 and C5, a mixed linear model will be performed with change from recovery in C2 and C5 concentration modeled as the response.

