### **Telephone Contact**

Patients were contacted by phone once/week to establish if all symptoms associated with URTI has abated. Once this had been confirmed the patients were booked in for a follow-up visit.

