### **Follow-Up/Early Withdrawal Visit**

Subjects returned within 4 weeks after treatment for a Follow-Up Visit once symptoms of URTI had abated. A series of full cough challenges were performed at this visit to determine reduction in cough hypersensitivity.

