### **5.3.2 Secondary Efficacy Endpoints**

Secondary endpoints that will be assessed include:

- Urge to cough (UTC) 30 min and 90 min post last cough challenge
- Cough severity Visual Analog Scale (VAS) 30 and 90 min post last challenge.
- To evaluate changes in cough reflex sensitivity during acute cough associated with URTI in relation to the healthy (post-recovery) state

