## **7.0 ANALYSIS POPULATION**

### **7.1 Full Analysis Set (FAS)**

All subjects who have taken at least 1 dose of study medication and provided at least 1 post-dose primary endpoint observation.

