## **10.5 Efficacy Analyses**

All efficacy analyses will be based on FAS set.

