| Study drug administration   |                        | X                |                      |                                       |                                       |                |
| Cough challenges citric acid, capsaicin, ATP, distilled water 30 min between challenges | X                      |                  |                      |                                       |                                       | X              |
| Abbreviated cough challenge 10 min between challenges.                                  |                        | X a   |                      |                                       |                                       |                |
| Urge-to-cough and cough severity VAS  | X                      | X b   |                      |                                       |                                       | X              |
| AE monitoring   |                        | X                | X                    | X                                     | X                                     | X              |
| Concomitant medications   | X                      |                  |                      |                                       |                                       | X              |
| Symptom monitoring  |                        |                  | X                    | X                                     |                                       |                |

a. Cough challenges begin 30 min and 90 min after dosing / each challenge separated by 10 min and in the same order as Baseline for each subject  
 b. Performed at 30 min and 90 min post treatment  
 #. Occurs same day as the successful completion of baselin

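### SAP 10.5.2 models change from recovery, so FAS subjects without a Follow-up value drop out; a model of LN values by visit would keep them

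*SAP*

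**What the plan says.** The secondary endpoint in SAP 5.3.2 is "To evaluate changes in cough reflex sensitivity during acute cough associated with URTI in relation to the healthy (post-recovery) state". For its analysis, 10.5.2 states that "a mixed linear model will be performed with change from recovery in" C2 and C5 concentration as the response. It does not name the acute time points, the fixed or random effects, or the handling of a missed visit.

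Section 10.5 says: "All efficacy analyses will be based on FAS set". Section 7.1 admits to the FAS any dosed subject who "provided at least 1 post-dose primary endpoint observation"; a Follow-up visit is not a condition.

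The recovery value comes from one visit. Under Telephone Contact, weekly calls establish whether symptoms have gone: "Once this had been confirmed the patients were booked in for a follow-up visit". The next section adds: "Subjects returned within 4 weeks after treatment for a Follow-Up Visit once symptoms of URTI had abated". Appendix A sets the window at Day 8 to Day 29. That visit is headed "Follow-Up/Early Withdrawal Visit", so it also serves subjects who leave early. Appendix A schedules the full challenge series only at Screening/Baseline and at FU/EW. The post-dose row reads "Abbreviated cough challenge 10 min between challenges".

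**The concern.** A change score exists only when both of its parts exist. Choosing it as the response discards the acute measurement of every subject who lacks a recovery measurement, although the SAP counts that subject in the analysis set. The usual reason to name a mixed model is that it can use such partial records, and a change-score response gives that up.

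At stake is the estimated shift in cough reflex sensitivity between illness and recovery. With 14 subjects, losing two removes one-seventh of the sample. The loss may not be random either, because the design ties having a Follow-up value to having recovered in time.

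**Working it through.** **The plan's own figure.** The only number available is 14 subjects (SAP 9.3). It comes with no effect size, SD, power or dropout rate, so there is nothing to reproduce, and every size below rests on assumed inputs.

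**Step 1: who enters the model.** FAS membership needs one dose and one post-dose primary observation. Change from recovery needs a Follow-up value. The only imputation rule for challenge data (9.2) covers a C5 that was not reached, not a missed visit. The analysed set is therefore FAS subjects with Follow-up, whichever acute time points are meant.

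**Step 2: what the model becomes.** Two readings were tried on simulated data for 14 subjects.
- Acute = pre-dose baseline: one change per subject, agent and endpoint. The model on the change and the paired t-test are identical (estimate 0.697, SE 0.230, t 3.04, p 0.0095 in both). A subject variance cannot be separated from the residual.
- Acute = baseline, 30 and 90 min: three changes per subject. With 3 of 14 Follow-up values missing, 33 rows from 11 subjects remain. The baseline contrast equals the paired mean (-0.658), but its SE is 0.355 against 0.290. This is not a paired test, yet the same 3 subjects are lost.

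**Step 3: scale.** On the capsaicin ladder in 5.1, a move from 0.3 to 1 µM is a change of 0.7 µM, and a move from 300 to 1000 µM is a change of 700 µM. On the LN scale both are ln(1/0.3) = ln(1000/300) = 1.20. Read literally, a change in concentration is dominated by subjects high on the ladder.

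**Step 4: size.** Let the shift be acute minus recovery in LN units (negative when the acute threshold is lower). Assume equal SD at both visits, correlation r, and linear relations. The alternative is a mixed model on the values, which predicts a missing recovery value from the acute value with slope r.

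- *Everyone returns:* the estimates are the same.
- *Random absence, n_c completers of 14:* neither is biased. The variance ratio, values model to paired change, is [(1 - r²)/n_c + (1 - r)²/14] / [2(1 - r)/n_c]. For r = 0.5 and n_c = 12 this is (0.0625 + 0.0179)/0.0833 = 0.96.

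| Absent | r = 0.3 | r = 0.5 | r = 0.7 |
|---|---|---|---|
| 2 | 0.95 | 0.96 | 0.98 |
| 4 | 0.90 | 0.93 | 0.96 |

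- *Absence depends on the acute value:* if the completers' acute mean is raised by δ, their recovery mean is raised by rδ. The paired change is biased by (1 - r)δ towards zero, and the values model by rδ - rδ = 0. Simulation (SD 1.5, shift -1.1, r = 0.5) gave paired biases of +0.12 with 2 absent (0.12/1.1 = 11%) and +0.25 with 4 absent (23%); the values model stayed within 0.02 of zero. This is strong selection: removing exactly the lowest acute values gives at most 0.18 and 0.34. With 12 completers the SE is 1.5 × √(2(1 - 0.5))/√12 = 0.43, so 0.12 is about 0.28 of an SE.
- *Absence depends on a low recovery threshold:* if the completers' recovery mean is raised by δ, their acute mean is raised by rδ. The paired bias is -(1 - r)δ and the values-model bias is -(1 - r²)δ, larger by the factor 1 + r. At r = 0.5 with 2 absent, simulation gave -0.11 against -0.16. Both overstate the shift, and the values model does so more.
- *Absence depends on a small change:* if selection moves the completers' mean change by Δ, half of it falls on each visit. The values model keeps (1 + r)/2 of the bias and removes (1 - r)/2, which is 35%, 25% and 15% for r = 0.3, 0.5 and 0.7. Simulation gave about 12% to 34%. Removing exactly the slowest subjects (r = 0.3 to 0.8) gave about 5% to 30%. Again both overstate the shift.

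**The case against.** A completers' paired comparison is conventional, and it is all that is needed if everyone attends Follow-up. The SAP does not say that anyone failed to. It also never states that acute means baseline only, so the equivalence with a paired test is conditional on that reading. Both points stand. The exclusion in Step 1 does not depend on the reading.

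A reader might infer more: that the slowest to recover are the absentees, so the planned analysis understates the shift and a values model corrects it. The documents do not support this. The booking rule and the Day 29 limit make such absence plausible, but the SAP gives no dropout figures or reasons. Because the visit doubles as the early-withdrawal visit, an unrecovered subject may have a challenge value there; the open question is then whether that value counts as recovery. If slow recovery did drive absence, the bias would run the other way. The shift would be overstated, and the values model would remove only part of the error or add to it. The shrinkage in Step 4 needs absence to depend on the acute threshold, which nothing in the SAP links to recovery speed.

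Nor is the values model's assumption simply the weaker one. It needs absence to depend only on observed values. The paired change needs absence to be unrelated to the change. Neither contains the other, which is why both results should be shown.

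**Conclusion.** The point holds in a limited form. As worded, 10.5.2 cannot be run on the FAS that 10.5 assigns to it, because every FAS subject without a Follow-up value is excluded and no rule covers the gap. If acute means the pre-dose baseline, the mixed model is in substance a completers' paired test. The concentration scale is also at odds with 10.5.1.

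The gain from a values model ranges from nil (full follow-up), through 2% to 10% of variance (random absence), to removal of a bias of about 11% to 23% of the effect (2 or 4 absent, strong acute-dependent selection, r = 0.5). It is partial or negative when absence follows the unseen recovery state. These sizes rest on assumed SD, shift, correlation and number absent. The consequence is confined to a secondary endpoint of an exploratory study in 14 subjects, so this is an inexpensive improvement and does not threaten the primary results.

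**What to change.** Replace the last sentence of 10.5.2 with wording to this effect:
- For each agent and endpoint, a mixed linear model is fitted to LN C2 or LN C5 values, with visit (pre-dose baseline, Follow-up) as fixed factor and subject as random effect. All FAS subjects with at least one of the two values are included.
- The acute-minus-recovery contrast is reported with its 95% CI.
- The completers' paired LN change is reported beside it as a sensitivity analysis, with the number of subjects who have no Follow-up value.
- Challenge values from an early-withdrawal visit in a subject who has not recovered are identified and not counted as recovery values.

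The cost is a few sentences of SAP text. No new data are needed, and SPSS, named in 9.0, fits the model. The change should be made before database lock, because 9.1 treats later undescribed analyses as post hoc. The price is reliance on absence depending only on observed values, and the paired result alongside is the safeguard.

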## 10.6 Safety Analysis

The safety analysis will utilize the Safety Population. Unless stated otherwise, all safety parameters will be summarized by baseline health status.

### 10.6.1 Adverse Events

Adverse events will be mapped to system organ classes and preferred terms using the MedDRA dictionary version 17.1. All adverse event summaries will be restricted to treatment emergent adverse events (TEAE), which are defined as those AEs occurring on or after dosing and those existing AEs worsening during the study. Adverse events will be summarized at onset of TEAE. Each TEAE will be assigned to a single treatment according to the date and time of onset. If an AE occurred during the wash-out period, the event will be counted under the treatment in Period 1. Then, if an AE occurred during 14-day follow-up post the Period 2, it will be counted under the treatment in Period 2.

For all AE tables, counting will be by subject and not by event within each period. In other words, if a subject has more than one event with the same preferred term in a given period, the subject will be counted once for that preferred term in the treatment group corresponding to that period. If a subject has more than one event in the same system organ class in a given period, the subject will be counted once for that system organ class in the treatment group corresponding to that period.

An overall summary of AEs will be presented. The overall summary will include the number and percentage of subjects experiencing any AEs, study drug related AEs, AEs by maximum severity, SAEs, study drug related SAEs, discontinued due to AE, and deaths. The number and percentage of subjects experiencing each AE, study drug related AE, and SAEs will be summarized according to system organ class and preferred term. An additional table including only preferred term summarized by treatment for the number and percentage of subjects experiencing each AE will be presented as well.

Complete subject listings of all AEs will be provided. For each AE the following will be specified: treatment group, start and stop dates, severity grade, MedDRA system organ class and preferred term, frequency, relationship to study treatment, action taken, outcome of the adverse event and seriousness.

#### Missing Severity or Relationship

Missing severity or relationship to study drug will prompt queries to be sent to the investigator to provide the information. If an event with missing severity cannot be resolved via query, severity

will imputed as severe. AEs with a missing relationship will be considered possibly/probably related for this summary.

#### Partial or Missing AE Start and Stop Dates

If the AE start date is incomplete, then it will be imputed as follows for the purpose of determining the onset of AE only:

In the event that the day portion (and only the day portion) of the AE onset date is missing:

- If the start date is completely missing, the start date will be equal to the first dose date. However, if the stop date is not missing and is before the first dose date, then the stop date will be used instead.
- If the start day is missing, the day of the first dose date will be used for the event occurring at the same month and year of the first dose date; otherwise, the first day of the month will be used.
- If the start day and month are missing, then the first day of the first month (January) will be used.

If the AE stop date is partial, then it will be imputed as follows for the purpose of determining the duration of AE only:

- If the stop date is completely missing and the event is not ongoing, the stop date will be equal to the last dose date or date of completion/withdrawal, whichever is the latest.
- If the stop day is missing, the day of the last study day will be used for the event stopping at the same month and year of the last study day; otherwise, the last day of the month will be used.
- If the stop day and month are missing, then the last day of the last month (December) will be used.

The aforementioned missing or partial data handling rules will be applied to the summary tables. The recorded missing or partial date values will be presented in the listings.

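### An adverse event dated only to the dosing year is imputed to 1 January, before dosing, and so is left out of the TEAE tables unless it is recorded as worsening, whereas an event with no start date defaults to the dose date

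*SAP*

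**What the plan says.** Section 10.6.1 confines every adverse event summary to TEAEs, which are "defined as those AEs occurring on or after dosing and those existing AEs worsening during the study". The subsection on partial and missing dates then gives three rules for an incomplete start date:

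- Nothing known: "If the start date is completely missing, the start date will be equal to the first dose date". There is one exception: "However, if the stop date is not missing and is before the first dose date, then the stop date will be used instead".
- Day not recorded: "the day of the first dose date will be used for the event occurring at the same month and year of the first dose date". In any other month the first of the month is used.
- Only the year known: "If the start day and month are missing, then the first day of the first month (January) will be used".

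The subsection limits these imputed dates to fixing the onset of the event and applies them to the summary tables. The listings keep the dates as recorded.

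The three rules stand under the line "In the event that the day portion (and only the day portion) of the AE onset date is missing", which describes only the second of them.

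**The concern.** TEAE status depends on onset relative to dosing, so the imputed start date decides whether an event reaches the tables. Two of the three rules go to the dose date when the recorded information leaves open whether the event began before or after dosing. The year-only rule does not. It sends the event to the start of the year, whatever the dose date and even if the recorded stop date is after dosing.

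The ordering is therefore odd. An event with no start information counts by default, while an event known to have begun in the dosing year is excluded by default. The default also runs against what the data collection would suggest: Appendix A marks adverse event monitoring from the treatment phase onward and not at Screening/Baseline, so a recorded event is more likely than not to have begun after dosing.

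Safety and tolerability is a listed objective (Section 2.2). At stake is an undercount in the TEAE tables, in one direction only.

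**Working it through.** The SAP states no figure on this point, so there is none to reproduce. The check applies the three rules as written.

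**Inputs.** TEAE definition: Section 10.6.1. Imputation rules: the subsection on partial and missing dates. Number of subjects: 14 (Section 3.0). Last follow-up day: Day 29 (Appendix A), which gives 29 possible onset days, Day 1 to Day 29. An onset on the day of dosing is treated as on or after dosing.

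**Step 1: the rules side by side.** Take a dose date D in year Y, an event that truly began after dosing, and no stop date before D.

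| Recorded onset | Imputed onset | TEAE by onset? |
|---|---|---|
| Nothing | D | Yes |
| Month and year of dosing | D | Yes |
| A later month and its year | First of that month, after D | Yes |
| Year Y only | 1 January of Y | No, unless D is 1 January |
| Year Y+1 only | 1 January of Y+1, after D | Yes |

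The fault is confined to the fourth row.

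**Step 2: how many dose dates are affected.** 1 January precedes D for 365 − 1 = 364 of 365 dose dates (365 of 366 in a leap year).

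**Step 3: classification of year-only events that truly began after dosing.** Cross every dose date with every onset from Day 1 to Day 29.

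- Combinations: 365 × 29 = 10,585 (366 × 29 = 10,614 in a leap year).
- Classed as TEAE because dosing was on 1 January: 29.
- Classed as TEAE because onset fell in the next calendar year, which is possible only for dosing on or after 4 December: 1 + 2 + … + 28 = 406.
- Total classed as TEAE: 29 + 406 = 435, and 435/10,585 = 4.1% (435/10,614 is also 4.1%).

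The rule for a wholly missing date and the rule for a missing day each class 100% of the same events as TEAE. The 4.1% assumes dose dates spread evenly over the year and onsets spread evenly over Days 1 to 29; the SAP gives neither distribution. It is also conditional on a year-only date having been recorded, and says nothing about how often that happens.

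**Step 4: effect on a table.** Section 10.6.1 counts subjects, not events. If a subject's only qualifying event in a row is excluded, that row falls by 1/14 = 7.1 percentage points, taking all 14 subjects as dosed. If the subject has another qualifying event in the row, it does not change.

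**Step 5: the rule under the change set out below.** With a year-only onset in the dosing year set to D, all 10,585 combinations are classed as TEAE, in line with the other two rules.

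**The case against.** The strongest objection is that the rule will hardly ever be used. There is one dosing day, a telephone contact at Day 8 with further calls if required, and a visit by Day 29. For the rule to apply, the month of onset would have to be unknown within a window that normally touches one or two calendar months. Nothing in the SAP suggests that even one such date is expected. This stands, and it keeps the point small.

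The second objection is that nothing disappears from the report. Section 10.6.1 provides complete listings of all adverse events with severity, relationship and seriousness. With 14 subjects a reader can find any event there. This also stands: only the summary tables are affected.

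Third, a reader might infer that every year-only event in the dosing year is lost. The text does not support that. An event moved to before dosing still qualifies if it is recorded as an existing event that worsened, and dosing on 1 January is a further exception.

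Fourth, a reader might see a breach of a conservative principle, since missing severity is imputed as severe and a missing relationship as related. Those are two specific rules. The SAP states no general principle that its date rules must follow, so the case rests on the inconsistency within the date rules themselves.

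Fifth, the lead-in could be read as disabling two of the three rules. The sentence directly above it covers any incomplete start date, and the rules name their own cases, so this is a wording slip.

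None of this justifies the year-only rule. It shows that the rule will rarely matter.

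**Conclusion.** The point holds, with small impact. The year-only rule puts onset before dosing for an event in the dosing year, unless dosing was on 1 January. The event then leaves the TEAE tables unless worsening of an existing event is recorded. The neighbouring rules set the dose date in comparable uncertainty. This is a stated rule that misclassifies, not an omission.

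The size is at most 7.1 percentage points for each affected subject in a table row, and zero where that subject has another qualifying event in the row. That assumes 14 dosed subjects. The number of year-only dates is unknown and should be very low.

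The stronger reading, that each lost event moves an incidence by 7.1 points or that events are concealed from the report, is not supported, because counting is by subject and the listings are complete.

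The similar 1 January rule for medication start dates (Section 10.4) does not share the fault: concomitant status there depends on the stop date as well as the start date.

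**What to change.** Replace the year-only rule with:

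> When only the year of onset is known and it is the year of dosing, use the dose date, unless a recorded stop date is before dosing, in which case use the stop date. When it is any other year, use 1 January of that year.

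As an editorial correction, reword the lead-in so that it covers any missing portion of the onset date.

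The stop-date rules need no change for this purpose. They serve only to derive duration, and Section 10.6.1 lists no table of duration, so limiting imputed stop dates to the end of participation would alter no listed summary.

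The cost is two lines of text and a small change in programming. The downside is that a vaguely dated event that began before dosing may occasionally be counted as a TEAE. The SAP already accepts that risk for wholly missing start dates.
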